APPENDIX C: IMPUTATION OF PARTIAL MISSING PRIOR THERAPY DATES

Prior therapy dates will be imputed if both month and year are present and only day is missing.

- For prior therapy start date, impute the first day of the month.
- For prior therapy end date, impute the last day of the month or 14 days before the first dose of study drug, whichever is earlier.
- For date of progression on prior therapy, impute the last day of the month or the day before study enrollment, whichever is earlier.

After imputation rules are applied, use the following algorithm to determine if a prior therapy is to be included in the analysis:

- For CPI:
 - Include all therapies in locally advanced/metastatic setting.
 - Include all therapies in neo-adjuvant/adjuvant setting that reason off therapy is PD or the best response to the therapy is PD.
 - Include all therapies in neo-adjuvant/adjuvant setting that date of progression or date of locally advanced/metastatic disease is within 3 months after therapy completion.
- For platinum-based therapy:
 - Include all therapies in locally advanced/metastatic setting.
 - Include all therapies in neo-adjuvant/adjuvant setting that reason off therapy is PD or the best response to the therapy is PD.
 - Include all therapies in neo-adjuvant/adjuvant setting that date of progression or date of locally advanced/metastatic disease is within 12 months after therapy completion.
 - If month is missing for either prior therapy end date or PD date but year is the same for both dates, include the therapy in the analysis.
- For non-CPI/non-platinum based therapy:
 - Include all therapies indicated as given in locally advanced/metastatic setting with the exception of intravesical treatment.

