8. Active hepatitis C infection or known human immunodeficiency virus (HIV) infection. Patients who have been treated for hepatitis C infection are permitted if they have documented sustained virologic response of ≥ 12 weeks.
9. Documented history of a cerebral vascular event (stroke or transient ischemic attack), unstable angina, myocardial infarction, or cardiac symptoms (including congestive heart

failure) consistent with New York Heart Association Class III-IV (see [Appendix C](#)) within 6 months prior to the first dose of enfortumab vedotin.

10. Radiotherapy or major surgery within 2 weeks prior to first dose of study drug.
11. Chemotherapy, biologics, investigational agents, and/or antitumor treatment with immunotherapy that is not completed 2 weeks prior to first dose of study drug.
12. Known hypersensitivity to enfortumab vedotin or to any excipient contained in the drug formulation of enfortumab vedotin (including histidine, trehalose dihydrate, and polysorbate 20).
13. Patients with active keratitis or corneal ulcerations. Patients with superficial punctate keratitis are allowed if the disorder is being adequately treated in the opinion of the investigator.
14. Other underlying medical condition that, in the opinion of the investigator, would impair the ability of the patient to receive or tolerate the planned treatment and follow-up.
15. Patients with uncontrolled diabetes. Uncontrolled diabetes is defined as hemoglobin A1c (HbA1c) $\geq 8\%$ or HbA1c $7-8\%$ with associated diabetes symptoms (polyuria or polydipsia) that are not otherwise explained.
16. Uncontrolled tumor-related bone pain or impending spinal cord compression. Patients requiring pain medication must be on a stable regimen at the time of enrollment (a minimum of 2 weeks).

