6.5 Handling of Dropouts and Missing Data

Missing data will not be imputed unless otherwise specified.

For time-to-event endpoints (e.g., duration of response, PFS, and OS), subjects who have no specified event will be censored as specified for each respective endpoint in Section 7.5.

Subjects who do not have at least two (initial response and confirmation scan) post-baseline response assessments will be counted as non-responders for the analysis of primary endpoint.

Missing AE dates will be imputed for the purpose of calculating duration of events and treatment-emergent status (see [Appendix A](#) for imputation details and [Appendix B](#) for treatment-emergent definition).

Missing prior therapy dates will be imputed for the purpose of calculating the time from prior therapy to first dose of study drug (see [Appendix C](#) for details).

Missing subsequent anticancer therapy start date will be imputed for the purpose of deriving the time-to-event endpoints as applicable (see [Appendix D](#) for details).

Unless otherwise specified, if the numeric value of a laboratory test is not available because it is below the lower limit of quantification (LLOQ), the result will be analyzed as equal to the LLOQ when a numeric value is required (e.g., calculating the mean) and be listed as “< LLOQ” in the listings.

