7.2 Demographic and Baseline Characteristics

Demographics and baseline characteristics, including age at consent, sex, ethnicity, race, baseline height, weight, body mass index, ECOG performance status, estimated creatinine clearance, hemoglobin A1c, smoking status, and Bellmunt risk factors will be listed and summarized with descriptive statistics for the full analysis set.

Disease specific characteristics, including time from diagnosis of locally advanced/metastatic disease to enrollment, histology, current extent of disease, disease stage, primary tumor location, and metastases sites will be listed and summarized for the full analysis set.

Summary of prior cancer-related therapies, including number of prior therapies, therapy type, setting of prior therapies, best response to prior therapies, time from most recent prior therapy to first dose of study drug, and prior cystectomy and nephrectomy, will be presented for the full analysis set.

In addition, the pre-existing conditions that are ongoing at baseline will be summarized.

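### SAP Appendix C can impute a prior-therapy end date outside the recorded month, giving a 14-day gap to first dose that the record rules out

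*SAP*

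**What the plan says.** SAP Appendix C applies where the day alone is unknown: "Prior therapy dates will be imputed if both month and year are present and only day is missing". For the end date the instruction is to "impute the last day of the month or 14 days before the first dose of study drug, whichever is earlier". The companion rule reads: "For prior therapy start date, impute the first day of the month". Appendix C gives the end date no lower limit, and no flag or query for a recorded month that conflicts with the result.

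SAP 6.5 gives the reason for the imputation: "Missing prior therapy dates will be imputed for the purpose of calculating the time from prior therapy to first dose of study drug". SAP 7.2 then lists "time from most recent prior therapy to first dose of study drug" among several descriptive items on prior treatment in the full analysis set. SAP 6.4.1 adds one day to an interval between two dates unless a section says otherwise.

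The 14-day cap matches the washout in Protocol 4.2. Criterion 11 covers chemotherapy, biologics, investigational agents and "antitumor treatment with immunotherapy that is not completed 2 weeks prior to first dose of study drug". Criterion 10 excludes "Radiotherapy or major surgery within 2 weeks prior to first dose of study drug".

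**The concern.** An imputed date should agree with the part of the date that is known. Here the month and year are known and only the day is missing, yet the rule can override the month. The cap equals the washout limit, so no imputed end date can fall less than 14 days before first dose, even when the recorded month makes 14 days impossible.

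At stake is the accuracy of the one interval that SAP 6.5 says the imputation serves. For the affected records the tabulated value is wrong, always in the direction of a longer gap. The derived data can also hold a therapy that ends before it starts.

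**Working it through.** The plan states no figure to reproduce, so this is date arithmetic on the rule as written.

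**Inputs.** End-date and start-date rules: SAP Appendix C. Two-week washout: Protocol 4.2, criteria 10 and 11. Plus-one convention: SAP 6.4.1. The calendar dates are illustrative.

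**Formulas.** Let F be the first-dose date, d its day of the month, and L the last day of the recorded end month.
- Imputed end: E = min(L, F − 14).
- Gap given by the rule: F − E, or F − E + 1 under SAP 6.4.1.
- Largest gap the record allows when the end month is the first-dose month: F − (first of that month) = d − 1, or d under SAP 6.4.1.

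**Step 1: end month equals first-dose month.** L is on or after F, so the cap always governs and E = F − 14. E leaves the recorded month when d − 14 < 1, that is d ≤ 14. The largest possible true gap is below 14 when d − 1 < 14, which is also d ≤ 14. The rule therefore leaves the recorded month on exactly the days when the washout cannot have been met.

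With the end recorded as May 2019, day unknown (plus-one values in brackets):

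| First dose | Imputed end | Gap from rule | Largest gap the month allows |
|---|---|---|---|
| 5 May | 21 Apr | 14 (15) | 4 (5) |
| 10 May | 26 Apr | 14 (15) | 9 (10) |
| 14 May | 30 Apr | 14 (15) | 13 (14) |
| 15 May | 1 May | 14 (15) | 14 (15) |

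In plus-one units the two-week limit prints as 15, so the conclusion is the same under either convention.

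**Step 2: conflict with the start-date rule.** If the start is also May 2019 with the day unknown, it is imputed as 1 May. With first dose on 10 May the end is 26 April, 5 days before the start.

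**Step 3: how far the problem extends.** The rule was applied to every first-dose date from 1 January 2018 to 31 December 2020 (365 + 365 + 366 = 1,096 dates).
- End month equal to first-dose month: the imputed date left the recorded month on 14 × 36 = 504 dates. These were the same 504 dates on which a breach was certain, with no mismatches.
- End month one month earlier: on month and year alone, no date left its month and none was a certain breach. For first dose 10 May and end in April, min(30 April, 26 April) = 26 April, which the record permits.

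The ratio 504/1,096 = 46% is a share of calendar days, conditional on a same-month, day-missing record existing. It is not a share of patients.

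**Step 4: where the date is used.** SAP 7.5 builds ORR on response assessments, runs DOR from first response, and runs PFS and OS from start of treatment. None uses the prior-therapy end date. Appendix C also applies 3-month and 12-month windows to decide which neoadjuvant or adjuvant therapies count. In the affected cases the imputed end is at most 14 days too early. Progression must precede entry (Protocol 4.1, criterion 4), so it falls within about two weeks of the imputed end, well inside both windows. What remains is the SAP 7.2 interval.

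**The case against.** The strongest reply is that the triggering record should hardly ever exist. Protocol section 4 does not let investigators waive criteria, Protocol 9.3.1.7 makes enrolment depend on meeting all criteria with sponsor approval, and Protocol 8.2 and 8.3 provide edit-check queries and source review. For a patient already accepted as meeting the washout, capping an unknown day at 14 days uses what is known. That argument stands where the month leaves compliance possible, including same-month records with first dose on day 15 or later. It fails where the month itself contradicts compliance. SAP 7.3 also plans to report eligibility exemptions, so the plan does not assume there will be none.

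The reply is also right about consequence. A reader might infer that the SAP 7.2 table is the trial's washout check, so that a breach would be hidden. The documents do not support that. SAP 7.2 gives the interval no compliance role, eligibility departures are reported under SAP 7.3, and nothing says deviation review uses imputed dates. The recorded month and year still show the breach.

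A reader might go further and infer that carry-over response from prior therapy is concealed and credited to enfortumab vedotin. That is not supported either. The efficacy endpoints do not use this date, patients must have progressed on or after their latest therapy, and any real carry-over depends on true dates, which no imputation rule alters.

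**Conclusion.** The rule is wrong in a narrow, well-defined case: a day-missing end date in the same calendar month as a first dose given on day 1 to 14. There it always yields a date outside the recorded month and a gap of 14 days (15 as SAP 6.4.1 would print it), when the truth is at most 0 to 13 (1 to 14). With first dose on the 5th, 10th or 14th, the gap is overstated by at least 10, 5 or 1 days (14 − 4, 14 − 9, 14 − 13).

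The effect is confined to one descriptive baseline interval. No efficacy conclusion changes. The number of affected patients cannot be derived from the documents and is probably very small, possibly zero. The finding rests on reading Appendix C literally, with no floor applied in programming that the SAP leaves unstated. It is a minor correction, worth making because the error always runs in the same favourable direction and costs almost nothing to remove.

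**What to change.** Add to the end-date rule in Appendix C: 'but not before the first day of the recorded month or the therapy start date'. Query every record where this floor applies. Assess it under SAP 7.3 from the recorded date, not the imputed one. Keep the resulting short gap in the SAP 7.2 summary.

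The floor selects the earliest date the record allows, so it is still the most favourable one, which is why the query matters. Same-month records with first dose on day 15 or later keep the 14-day cap unless the therapy start date is later than the capped date. On those records a breach is possible but not established.

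The cost is one clause, a small program change and perhaps a few queries. The minimum in the SAP 7.2 table may look slightly less favourable. SAP section 1 allows the change by amendment before database lock, or by documentation in the study report.

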4.1 Inclusion Criteria

1. Patients must have histologically documented urothelial (previously known as transitional cell) carcinoma (i.e., cancer of the bladder, renal pelvis, ureter, or urethra). Patients with squamous differentiation or mixed cell types are eligible. Patients with resectable locally advanced disease are ineligible.
2. Patient must have received prior treatment with a CPI in the locally advanced or metastatic urothelial cancer setting. Patients who received CPI therapy in the neoadjuvant/adjuvant setting and had recurrent or progressive disease either during therapy or within 3 months of therapy completion are eligible. A CPI is defined as a PD-1 inhibitor or PD-L1 inhibitor (including, but not limited to: atezolizumab, pembrolizumab, durvalumab, avelumab, and nivolumab).
3. Patients must be one of the following:
 - a. Platinum-treated (Cohort 1): Patients who received prior treatment with platinum-containing chemotherapy defined as those who received platinum in the adjuvant/neoadjuvant setting and had recurrent or progressive disease within 12 months of completion OR received treatment with platinum in the locally advanced (defined as unresectable with curative intent) or metastatic setting;

OR

- b. Platinum-naïve and cisplatin ineligible (Cohort 2): Patients who have not received prior treatment with platinum-containing or other chemotherapy in the locally advanced or metastatic setting and are ineligible for treatment with cisplatin at time of enrollment due to one of the following: ECOG performance status score of 2; impaired renal function (defined as creatinine clearance [CrCl] ≥ 30 and < 60 mL/min),

or a \geq Grade 2 hearing loss. Patients who received platinum in the adjuvant/neoadjuvant setting and did not progress within 12 months of completion will be considered platinum-naïve.

4. Patients must have had progression or recurrence of urothelial cancer during or following receipt of most recent therapy.
5. Tumor tissue samples must be available for submission to the sponsor prior to study treatment.
6. Legally an adult according to local regulation at the time of signing informed consent, and minimum age of 18 years.
7. Patients must have measurable disease according to RECIST (Version 1.1) ([Eisenhauer 2009](#)). Lesions in a prior radiation field must have progressed subsequent to radiotherapy to be considered measurable.
8. An ECOG performance status score of ≤ 1 for Cohort 1, or ≤ 2 for Cohort 2.

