6.8 Examination of Subgroups

As exploratory analyses, subgroup analyses will be conducted for selected endpoints.

Subgroup analyses to be conducted are:

- Age (<65, \geq 65 years old)
- Age (<75, \geq 75 years old)
- Sex (female, male)
- Race (white, non-white)
- ECOG performance score at baseline (0, 1-2)
- Bellmunt risk score (0-1, \geq 2) ([Bellmunt 2010](#))
- Baseline weight (\leq 100, $>$ 100 kg)
- Primary tumor sites (upper tract, bladder/other)
- Liver metastasis (yes, no)
- Number of prior systemic therapy in locally advanced or metastatic setting (1-2, \geq 3)

- Best response to prior CPI (responder, non-responder)
- PD-L1 CPS ($<10, \geq 10$)

A subgroup analysis may not be performed if the number of subjects in the subgroup is not sufficiently large (i.e., $<10\%$ of the full analysis set for a given cohort). At the time of the primary analysis of Cohort 1, subgroup analysis will be performed for Cohort 1 only, without including Cohort 2 subjects.

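### SAP Appendix C tests the 3-month and 12-month prior-therapy windows on a progression date imputed to month-end, so a perioperative therapy that qualified the patient can drop out of the prior-therapy analyses

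*SAP*

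**What the plan says.** SAP Appendix C imputes prior-therapy dates when only the day is missing. For progression: "For date of progression on prior therapy, impute the last day of the month or the day before study enrollment, whichever is earlier". For the end of therapy: "For prior therapy end date, impute the last day of the month or 14 days before the first dose of study drug, whichever is earlier". The order of steps is explicit: "After imputation rules are applied, use the following algorithm to determine if a prior therapy is to be included in the analysis".

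For a neo-adjuvant or adjuvant checkpoint inhibitor (CPI), the date test is "date of progression or date of locally advanced/metastatic disease is within 3 months after therapy completion". For platinum it is "date of progression or date of locally advanced/metastatic disease is within 12 months after therapy completion". Either therapy is also counted, without any date, if PD was the reason for stopping it or the best response to it. Therapy given in the locally advanced or metastatic setting is always counted. No rule retains a therapy because it was the one that qualified the patient.

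Protocol 4.1 applies the same windows at entry. Under criterion 2, patients with perioperative CPI who "had recurrent or progressive disease either during therapy or within 3 months of therapy completion are eligible". Criterion 3a gives perioperative platinum 12 months, and criterion 3b treats patients without progression in that time as platinum-naïve.

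SAP 6.5 gives the purpose of imputing prior-therapy dates only as computing the time from prior therapy to first dose. It does not mention deciding which therapies count.

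**The concern.** Month-end is the latest day the known month allows. With a complete therapy end date, imputing it can move progression out of the window but never into it. A patient correctly enrolled on adjuvant CPI could be tabulated without that CPI, and a Cohort 1 patient without the platinum that placed them there.

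Appendix C does not name the outputs it governs. On a natural reading they are:
- the prior-therapy summary in SAP 7.2;
- the SAP 6.8 subgroups by best response to prior CPI and by "Number of prior systemic therapy in locally advanced or metastatic setting";
- the time-to-response comparison by prior-CPI response in SAP 7.5.1.

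A Cohort 2 patient whose only counted therapy was perioperative CPI would fall to zero prior therapies, outside both the 1-2 and the ≥3 category. In a trial whose population and cohorts are defined by prior therapy, such tables would contradict the enrollment record.

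**Working it through.** Appendix C states no figure to reproduce, so the check applies its rules to dates.

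**Inputs.** Windows of 3 and 12 months (Protocol 4.1, SAP Appendix C); month-end imputation (Appendix C); durations as end − start + 1 days and months as days/30.4375 (SAP 6.4.1). Appendix C does not say whether its windows use that conversion or calendar months, so both were tried.

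**Worked cases.**
- CPI ended 10 Jan 2017, true progression 5 Apr 2017: 85 days, (85+1)/30.4375 = 2.83 months, inside. Recorded as April with no day, it becomes 30 Apr: 110 days, (110+1)/30.4375 = 3.65 months, outside.
- Platinum ended 10 Jan 2017, true progression 5 Jan 2018: 360 days, 361/30.4375 = 11.86 months, inside. Imputed to 31 Jan 2018: 386 days, 387/30.4375 = 12.71 months, outside.

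**Approximate share.** If therapy ended on day d, the window closes on day d of the closing month, and progression on days 1 to d of that month is pushed out unless d is month-end. In a 30-day month the average number of lost days is (1+2+…+29)/30 = 14.5. Dividing by the window length:
- 3 months: 14.5/(3 × 30.4375) = 14.5/91.3 ≈ 16%
- 12 months: 14.5/(12 × 30.4375) = 14.5/365.25 ≈ 4%

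**Full enumeration.** Every end date in 2015-2017 was paired with every progression date in the window, equally weighted, with no cap binding and no other route open. Share of truly in-window records dropped:

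| Window | Month convention | End day known | End day also missing |
|---|---|---|---|
| 3 months | calendar | 16.0% | 4.0% |
| 3 months | (days+1)/30.4375 | 16.4% | 12.7% |
| 3 months | days/30.4375 | 16.2% | 9.7% |
| 12 months | calendar | 4.0% | 0.1% |
| 12 months | (days+1)/30.4375 | 4.0% | 4.0% |
| 12 months | days/30.4375 | 4.0% | 1.4% |

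When both days are missing, both dates move to month-end and the shifts partly or largely cancel, except for the 12-month window under the +1 convention.

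**First-of-month imputation, for comparison.** With the end day known it drops none, but it wrongly counts about 24-25% of progressions in roughly the 60 days after the window.

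**Scale.** The documents do not give the number of day-missing records. Per 10 in-window records with a complete end date, the expected loss before any rescue is 10 × 0.16 = 1.6 for CPI and 10 × 0.04 = 0.4 for platinum.

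**The case against.** The strongest reply is that these shares are ceilings. They ignore the enrollment cap and the other routes. One route is a locally advanced or metastatic disease date inside the window; SAP 7.2 uses the date of that diagnosis for the whole full analysis set, so it should usually be on file. Progression during therapy is kept when PD is the reason for stopping or the best response. The month-end rule for therapy end dates also pushes toward inclusion, so Appendix C as a whole does not err in one direction. All of this stands and limits the point. None of it guarantees that a qualifying therapy is kept.

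Three stronger readings are tempting but unsupported.

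- **That the primary result is at risk.** The full analysis set (SAP 5.1) requires only enrollment and treatment, and the primary ORR uses it. Appendix C removes a therapy record, not a patient, and does not reassign cohorts.
- **That Appendix C contradicts itself.** Its platinum rules contain one that begins: "If month is missing for either prior therapy end date or PD date but year is the same for both dates, include the therapy in". Such a record is counted, which can look more generous to a missing month than to a missing day. But progression later in the same calendar year as therapy end is within 12 months, so the rule is a deduction. Same-year records missing only the day also pass by calendar months. The one exception is 1 January to 31 December of a leap year under the +1 convention: 366/30.4375 = 12.02. The losses described here cross a year boundary, where the month-missing rule does not apply.
- **That patients would commonly fall to zero prior therapies.** Every counted therapy would have to be dropped. In Cohort 1 both CPI and platinum would have to be perioperative and both fail the test.

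Testing with the first of the month is not a sound remedy either. Besides the over-inclusion shown above, it could give a Cohort 2 patient, platinum-naïve under criterion 3b, a counted platinum therapy.

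**Conclusion.** The rule is wrong as written, with low impact. A perioperative CPI or platinum therapy that met inclusion 2 or 3a can be left out of the prior-therapy outputs when the progression day is missing, progression fell in the window's closing month, the enrollment cap does not bring the date back inside, and no other route applies.

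The conditional loss is about 16% (CPI) and 4% (platinum), assuming uniform progression, a complete end date and no rescue. With the end day also missing it is about 4% and 0.1% by calendar months, and up to 12.7% and 4.0% under the SAP's +1 convention. These are shares of day-missing, truly in-window records, not of trial patients. The trial-level count is unknown and probably small. Only descriptive or exploratory outputs can change. Severity: minor.

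**What to change.** In SAP Appendix C, state that when the progression day is missing, perioperative CPI or platinum is classified by the recorded eligibility and cohort determination (inclusion 2, 3a, 3b), not by the imputed date. A therapy accepted as qualifying is then always counted, and platinum in a patient enrolled as platinum-naïve is not. Keep month-end imputation for descriptive intervals only, in line with the purpose in SAP 6.5.

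The cost is two or three sentences and a small programming change. It avoids the over-inclusion of a first-of-month test. One detail needs settling: if another therapy already met the criterion, the eligibility record may not rule on a perioperative one, and Appendix C should say how that record is handled. Stating whether the windows are calendar months or days/30.4375 would also help, since the both-days-missing results depend on it.
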